5.7.1.1. Sensitivity of the Primary Efficacy Analysis

Robustness of the primary analysis statistical methods will be assessed through sensitivity analyses, including a different methodology for missing data (e.g., pattern mixture model to assess the potential violation of the missing at random assumption) and on-treatment analysis for more clinically relevant treatment comparisons of the percent change in calculated LDL-C from

baseline to week 24 (i.e., mITT patient population using calculated LDL-C values collected during the efficacy treatment period [on-treatment estimand]).

Sensitivity to Stratification at Randomization

To assess the robustness of the primary analysis to stratification mistakes made at the time of randomization (i.e. the stratum recorded in IVRS/IWRS differs from the actual stratum recorded in the e-CRF), the MMRM model will be re-run replacing the IVRS/IWRS strata with the e-CRF actual strata.

Sensitivity to On-treatment Calculated LDL-C Values

To assess the robustness of more clinically relevant between group comparisons for the analysis of the primary efficacy endpoint, the same statistical analysis method approach as described above in Sec 5.7.1 will be applied in the mITT population. The intent-to-treat estimand will be replaced by the on-treatment estimand, which is defined as all LDL-C values collected during the efficacy treatment period (Sec 3.1.2).

Sensitivity to Non-Good Clinical Practice (GCP) Compliant Sites

To assess the impact of non-GCP compliance sites on the primary efficacy endpoint, the primary efficacy analysis will be performed excluding non-GCP compliant sites. Sites known to be non-GCP compliant at the time of database lock will be identified for this analysis before database lock. Any additional sites determined to be non-GCP compliant post-database lock will be separately identified.

Sensitivity to the Handling of Missing Data

Sensitivity analyses will be conducted to assess the robustness of primary efficacy analysis with regards to the handling of missing data ([Little RJ 2012](#)).

Visual examination

- In order to explore the missing data pattern, post-baseline calculated LDL-C observations (in the ITT population) will be described according to the following groups:
 1. Calculated LDL-C available at week 24 (i.e. primary efficacy endpoint available),
 2. Calculated LDL-C available at week 20 but missing at week 24,
 3. Calculated LDL-C available at week 16 but missing from week 20,

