 4. Calculated LDL-C available at week 12 but missing from week 16,
 5. Calculated LDL-C available at week 8 but missing from week 12,
 6. Calculated LDL-C available at week 4 but missing from week 8,
 7. Calculated LDL-C available at week 2 but missing from week 4,
 8. Calculated LDL-C missing from week 2.

A graph of mean percent change from baseline calculated LDL-C levels \pm SE at baseline, and at weeks 2, 4, 8, 12, 16, 20, and 24 will be provided by missing data pattern, for each treatment group.

- In the ITT population, demographic and baseline lipids will be described within the missing data pattern number 1 above versus the remaining missing data patterns above. P-values from Fisher exact test for categorical data and from asymptotic one-way ANOVA test for Wilcoxon scores (Kruskal-Wallis test) for continuous data, will be also provided, for descriptive purposes.

Pattern mixture model (PMM)

The MMRM model relies on the “missing-at-random” (MAR) assumption. Because the possibility for a not-missing-at-random (NMAR) missingness mechanism can never be excluded, sensitivity analysis to explore the impact of non-ignorable missingness on the primary efficacy analysis will be conducted using the PMM approach as described below (see Appendix 10.8 for more details).

In the PMM approach, different imputation strategies will be applied to calculated LDL-C values missing during the double-blind on-treatment period (i.e. within the time period from the first double-blind study treatment administration up to the day of last double-blind administration +35 days) versus calculated LDL C values missing due to treatment discontinuation after the on-treatment period (i.e. after the day of last double-blind administration +35 days) based on the following assumptions:

- Patients within 35 days of their last double-blind study treatment administration would continue to show benefit from treatment similar to that observed at the scheduled time point. Therefore, LDL-C values missing during the on-treatment period (e.g., samples obtained out-side the specified window, no blood sample available although visit was performed, etc.) should be considered “Missing at Random” and imputed based on other observed measurements in the on-treatment period.

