- Patients who stopped taking their study treatment no longer benefited from it after discontinuation, and thus tended to have LDL-C values returning to baseline. Therefore, LDL-C values missing after the on-treatment period should be imputed based on patient’s own baseline value.

Missing data from the randomized population will be imputed 100 times to generate 100 complete data sets, using the SAS MI procedure (using Markov Chain Monte Carlo). The 100 completed datasets of observed and imputed LDL-C data will be used for the sensitivity analysis of the primary efficacy analysis method.

For the percent change from baseline calculated LDL-C endpoint, the 100 complete datasets of observed and imputed LDL-C data at week 24 will be analyzed using an ANCOVA model with treatment group and randomization strata as fixed effect, and the baseline LDL-C value as continuous covariate. The SAS MIANALYZE procedure will be used to generate valid statistical inferences by combining results from the 100 analyses using Rubin’s formulae.

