10.7. Detailed Description of the Multiple Imputation Procedure

The following is a detailed description of the multiple imputation procedure which will be used for analysis of the secondary efficacy endpoints.

In general, the missing pattern is anticipated to be not monotone, a two-step approach will be used:

- Step 1: the MCMC method will be used in conjunction with the IMPUTE=MONOTONE option to create an imputed data set with a monotone missing pattern. Set the SEED=1629 option in SAS MI procedure.
- Step 2: Using the monotone data set from step 1, missing data will be imputed using the regression method. Set the SEED=9261 option in SAS MI procedure.

The imputation model for step 1 will include the treatment group and the values of the analyzed parameter at baseline and planned time-points up to week 24.

The imputation model for step 2 will include the same variables as in step 1 with the following additional variables:

- the randomization strata (apheresis treatment status strata);
- age, BMI, and gender (age and BMI included as continuous variables).

Non-continuous variables included in the imputer's model (i.e., treatment group, randomization strata and gender) are not expected to be missing.

In addition, for continuous efficacy variables anticipated to have a non-normal distribution (i.e. TG and Lp(a)), data will be log-transformed before imputation process and then back-transformed to create the imputed data sets using the TRANSFORM statement of SAS MI procedure.

For variables other than those continuous efficacy variables anticipated to have a non-normal distribution (i.e. TG and Lp(a)), for each simulation leading to negative imputed value, another value will be redrawn using MINIMUM option of SAS MI procedure.

The number of imputations (100) will be informally verified by replicating sets of 100 imputations and checking whether the combined results are stable. If not stable, the number of imputations will be increased and informally checked as above, and thus continued until stable estimates are obtained.

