10.8. Detailed Description of Pattern Mixture Model

As a sensitivity analysis of the primary efficacy endpoint (i.e. percent change from baseline to Week 24 in LDL-C), a pattern-mixture model approach will be used, with a different imputation strategy applied for missing LDL-C values during the on-treatment period (i.e. within the time period from the first double-blind study treatment administration up to the day of the last double-blind study treatment administration +35 days or to the day before the first open-label study treatment administration, whichever comes first) and missing LDL-C values after treatment discontinuation (i.e. after the day of last study treatment administration +35 days) based on the following assumptions:

- Patients within 35 days of their last study treatment administration would continue to show benefit from treatment similar to that observed at the scheduled time point. Therefore, LDL-C values missing during the on-treatment period will be considered “Missing at Random” and imputed using a model estimated using all samples collected on treatment.
- Patients who stopped taking their study treatment no longer benefited from it in the future, and thus tended to have LDL-C values returning to baseline. Thus LDL-C values missing after treatment discontinuation will be imputed based on patient’s own baseline value.

The assumptions for this approach are based on the following considerations:

- Missing values during the on-treatment period are mostly consecutive to:
 - Visits performed outside of the pre-specified time-window
 - No blood sample available although visit was done
 - LDL-C not measurable due to technical reasons

In addition, these missing data are often intermittent, i.e. followed by LDL-C values collected at subsequent visits. It is therefore considered reasonable to assume that these missing data were “At Random”.

Missing LDL-C values will be imputed 100 times to generate 100 complete data sets. The percent change from baseline to Week 24 will be derived from observed and imputed LDL-C at this time point. The completed data sets will be analyzed using an analysis of covariance (ANCOVA) model with treatment group and randomization strata as fixed effects, and the baseline LDL-C value as continuous covariate. The results from the 100 analyses will be combined using Rubin’s formulae. If necessary, the number of imputations (100) will be increased until stable estimates are obtained.

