Imputation of missing data during the on-treatment period

Missing LDL-C values during the on-treatment period will be imputed from other on-treatment measurements assuming Missing At Random, using SAS® MI procedure.

Only LDL-C values collected during the on-treatment period will be included in the imputation model. This way, missing LDL-C values during the on-treatment period will be imputed based solely on observed on-treatment LDL-C values.

The imputation model will include the treatment arm, baseline LDL-C value, and all LDL-C values at pre-specified visits. Since the pattern of missing data will necessarily be non-monotone, a Monte-Carlo Markov Chain (MCMC) method will be used. A minimum value of 0 will be specified in order to avoid negative imputed LDL-C values.

A sample SAS code is provided below:

```
proc mi data=DATAIN out=DATAOUT nimpute=100 minimum=. 0 0 0 0 0 0 0 0 seed=1629;  
  mcmc impute=monotone;  
  var ARM LDL_BASE LDL_W2 LDL_W4 LDL_W8 LDL_W12 LDL_W16 LDL_W20  
  LDL_W24;  
run;
```

As stated above, the input dataset DATAIN will include only LDL-C values collected during the on-treatment period. Any LDL-C values collected during the post-treatment period will be excluded from the input dataset. In practice, the MI procedure will generate imputed values for all missing values (whether on-treatment or post-treatment), but only imputed values during the on-treatment period will be kept in the final datasets that will be analyzed using ANCOVA. Imputed values during the post-treatment period will be discarded and replaced by imputed values described in the next paragraph.

Imputation of missing data after treatment discontinuation

Missing LDL-C values during the post-treatment period will be imputed assuming LDL-C values would on average return to baseline values.

For each patient, missing post-treatment LDL-C values will be imputed 100 times, using a random draw from a normal distribution (SEED=9261), with mean equal to patient's own baseline value and variance equal to the conditional variance at the specific time-point, given the baseline value.

Let Y_0 and Y_1 denote the LDL-C at baseline and at the specific time-point respectively. Since Y_0 and Y_1 are assumed to have a bivariate normal distribution, the conditional variance of Y_1 given Y_0 is:

$$Var(Y_1|Y_0 = y_0) = \sigma_1^2(1 - \rho^2)$$

Where σ_1^2 denotes the variance of Y_1 and ρ the coefficient of correlation between Y_0 and Y_1 .

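### The sample code for the pattern-mixture sensitivity analysis (SAP 10.8) leaves an on-treatment missing week-24 LDL-C unfilled, and 10.8 and 5.7.1.1 disagree on whether the first open-label dosing day is on-treatment

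*SAP*

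**What the plan says.** SAP 5.7.1.1 and Appendix 10.8 describe a pattern-mixture model as the check on the missing-at-random assumption behind the primary MMRM. LDL-C values missing on treatment are imputed as missing at random from other on-treatment values. Values missing after treatment has stopped are drawn around the patient's own baseline.

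**What the text promises.** Appendix 10.8 states: "Missing LDL-C values will be imputed 100 times to generate 100 complete data sets". It adds that "the MI procedure will generate imputed values for all missing values (whether on-treatment or post-treatment"), with the post-treatment ones then replaced by the baseline-centred draws. Section 5.7.1.1 says that "the 100 complete datasets of observed and imputed LDL-C data at week 24 will be analyzed using an ANCOVA model".

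**What the code does.** The single PROC MI call in 10.8 specifies "mcmc impute=monotone". Its variable list runs from arm and baseline through weeks 2 to 20 and ends with week 24. No second imputation step follows for on-treatment values.

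**What Appendix 10.7 says about the same option.** For the secondary endpoints, step 1 uses it "to create an imputed data set with a monotone missing pattern". In step 2, "missing data will be imputed using the regression method".

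**On-treatment period.** Section 5.7.1.1 runs it "up to the day of last double-blind administration +35 days". Appendix 10.8 ends it at the earlier of that day and the day before the first open-label dose, and its other branch begins only after +35 days. Section 3.1.2 (mITT) ends the efficacy treatment period at the first open-label dose itself. The week-24 window in Table 2 of Appendix 10.2 includes the first open-label dosing day.

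**The concern.** The ANCOVA uses week 24 only, and week 24 is the one visit that the sample code can never fill. The pattern concerned is among those that 5.7.1.1 sets out to describe: "Calculated LDL-C available at week 20 but missing at week 24". Patients still on treatment but without a week-24 sample would be omitted from all 100 analyses instead of being imputed as the text intends. SAS need not stop with an error, because the ANCOVA simply omits records with no response.

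The second problem makes the first harder to repair. Appendix 10.8 admits only on-treatment values to the imputation model. Read literally, its cut at the day before open-label dosing removes the scheduled, observed week-24 samples of patients entering the open-label period. That would leave little week-24 data from which to estimate the imputation model, even with the code option corrected.

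**Working it through.** **1. Can the code fill week 24?** Under a monotone completion, a missing value is filled only if a later variable in the list is observed. Take baseline as observed and let each of the seven visits (weeks 2, 4, 8, 12, 16, 20, 24) be observed or missing. That gives 2^7 = 128 patterns.

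- Week 24 is missing in 64 of them and is filled in 0 of 64.
- Gaps at earlier visits that are followed by an observed value are filled.
- Full-chain MCMC, or a 10.7-style regression step, fills week 24 in all 64.

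**2. Which branch holds the first open-label dosing day?** Inputs from the schedule of events: last double-blind dose on day 141 ±5, first open-label dose on day 169 ±1. The week-24 sample is drawn before that dose at the same visit.

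| | On-treatment ends (on schedule) | Day 169 |
|---|---|---|
| 5.7.1.1 | 141 + 35 = day 176 | on-treatment |
| 10.8, on-treatment branch | earlier of 176 and 169 − 1 = day 168 | not on-treatment |
| 10.8, other branch | starts after day 176 | not post-treatment |
| 3.1.2 | first open-label dose, day 169 | included up to the dose |

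Across the visit windows the gap from last double-blind dose to first open-label dose is 168 − 146 = 22 days to 170 − 136 = 34 days, always inside 35. So in all 11 × 3 = 33 combinations of dosing days, exactly one day of the week-24 window, the open-label dosing day, falls in neither branch of 10.8. Under 5.7.1.1 no day does. Patients who do not enter the open-label period have no gap.

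**3. How many patients?** The documents give no on-treatment missing rate for week 24. The nearest figures are the planning rates in SAP 2.2: 5% non-evaluable and 15% dropout. Neither is strictly this rate, so 2%, 5% and 10% are assumptions.

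Patients who stop before the week-20 dose belong to the return-to-baseline branch: a last dose at week 16 gives 113 + 35 = day 148, before the window opens on day 155. If 15% stop that early, 57 × 0.85 = 48.45 patients remain exposed to the problem.

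| Assumed missing rate | Affected, 15% early stopping | Affected, none | P(at least one), 48 exposed |
|---|---|---|---|
| 2% | 48.45 × 0.02 = 0.97 | 57 × 0.02 = 1.1 | 1 − 0.98^48 = 0.62 |
| 5% | 48.45 × 0.05 = 2.4 | 57 × 0.05 = 2.9 | 1 − 0.95^48 = 0.91 |
| 10% | 48.45 × 0.10 = 4.8 | 57 × 0.10 = 5.7 | 1 − 0.90^48 = 0.99 |

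**4. Effect on precision.** The standard error of the difference is proportional to √(1/n_E + 1/n_P), with 38 and 19 planned. Relative to complete data:

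- 1 lost, in proportion to allocation: √(57/56) = 1.009
- 5 lost, in proportion: √(57/52) = 1.047
- 1 lost, evinacumab: √[(1/37 + 1/19)/(1/38 + 1/19)] = 1.004
- 5 lost, all placebo: √[(1/38 + 1/14)/(1/38 + 1/19)] = 1.113

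**The case against.** The best defence is that the code is only a sample, while the prose states the required result: complete data sets in both 5.7.1.1 and 10.8, and values for every gap in 10.8. An analyst who follows the prose gets the right analysis, and unfilled week-24 values would show up on inspection. The intent is indeed clear. But the code is the most specific instruction given, and the repair is not specified. Full MCMC and the 10.7 regression step are different imputation models, because the latter adds apheresis stratum, age, BMI and gender. Nor is a second step implied: 10.8 uses seed 1629, which 10.7 gives to step 1, and assigns 9261, the seed of step 2 in 10.7, to the return-to-baseline draws.

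Several points on size stand:

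- The eight patterns in 5.7.1.1 are an exhaustive list, not a forecast. Appendix 10.8 itself says on-treatment gaps are often intermittent, and those the code does fill.
- Nothing in the documents supports a rate as high as 10%.
- If five patients were lost at random, the chance that all were placebo is C(19,5)/C(57,5) = 11,628/4,187,106 = 0.28%, so the 11% figure is a bound.
- Correct imputation would not recover all the lost information, so the cost of the defect itself is smaller than the complete-data comparison suggests.

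On the period definitions, 5.7.1.1 refers to 10.8 for detail and never mentions open-label dosing. A missing value has no collection day. It belongs to a window that is on-treatment under 10.8 for all but its last day, and a patient taking the open-label dose has not discontinued. All this is fair, and it means the conflict bears mainly on which observed samples feed the imputation model. There, 10.8 points both ways: it admits only on-treatment values, yet the exclusion it spells out names only post-treatment ones. The text needs settling.

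**Conclusion.** Both parts hold. As written, the sample code in 10.8 cannot produce the completed week-24 data that 10.8 and 5.7.1.1 require. The two sections also classify the scheduled week-24 sampling day differently.

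The consequence is minor. Under the assumed missing rates, about 1 to 5 of 57 patients would be left out of one sensitivity analysis, with a standard error about 0.9% to 4.7% above complete data if losses follow the 2:1 allocation. Bias is likely to be small if on-treatment gaps arise mostly from visit timing and technical causes, as 10.8 supposes. The primary MMRM, the return-to-baseline branch, the observed week-24 values in the ANCOVA and the testing hierarchy are not affected. No effect size can be put on the period conflict, because it depends on which reading of 10.8 is programmed.

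**What to change.** In Appendix 10.8, replace the monotone option with `impute=full`. This is preferable to adding the second step of 10.7, because it keeps the imputation model that 10.8 describes. If the 10.7 step is chosen instead, 10.8 should say so and list the extra covariates.

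Use one on-treatment definition in 5.7.1.1 and 10.8: from the first double-blind dose to the earlier of the last double-blind dose +35 days and the first open-label dose, with the pre-dose sample on that day counted as on-treatment. This agrees with Section 3.1.2 and Table 2. State explicitly that such samples enter the imputation data set. Both changes are needed: the code change alone leaves open which week-24 values inform the model.

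The cost is one code option and one harmonised sentence, made before the first-step database lock. No new data are needed.

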10.9. Schedule of Time and Events

Schedule of Events – Run-in and Screening

Study Procedure	Run-in ⁷	Screening
Visit	1a	1
Day	-70 to -14	-14 to -1
Visit Window (Day)		
Week	-10 to -2	-2 to -1
Screening/Baseline:		
Informed Consent	X	
[REDACTED]		X
Inclusion/Exclusion		X
Medical/Surgical History, Alcohol/Smoking Habits		X
Medication History		X
Demographics		X
Treatment:		
Concomitant Medications (including LMT and apheresis)	X	X
Query LMT Compliance	X	X
Efficacy:		
Lipid Panel ^{1,2}		X
Safety:		
Adverse Events	X	X
Physical Examination		X
Measured Height		X
Body Weight		X
Vital Signs (pulse rate, BP)	X	X
Electrocardiogram ³		X
Tanner stage ⁴		X
Laboratory Testing⁵:		
Hematology		X
Blood Chemistry		X
Creatine Phosphokinase		X
Hepatitis B Surface Antigen		X
Hepatitis C Antibody		X
Serum Pregnancy Test ⁶		X
Urine Pregnancy Test ⁶	X	
FSH	X	
Sex Hormones ⁴		X
Urinalysis		X
TSH		X
DNA sample for HoFH genotyping		X
Other:		
Review of diet	X	X

Footnotes for Schedule of Events – Run-in Period

1. Study assessments will be performed and blood samples will be collected before the dose of study drug in all patients. For patients undergoing apheresis: Study assessments will be performed and blood samples will be collected immediately before the lipid-apheresis procedure; study drug will be administered after the apheresis procedure.

2. Fasting sample will be collected for the lipid panel: TC, calculated LDL-C, HDL-C, TG, non-HDL-C
3. ECG should be performed before blood samples are collected at visits requiring blood draws.
4. Assessment of Tanner Stage and sex hormones (includes luteinizing hormone, follicle stimulating hormone, estradiol, total testosterone) only applicable to patients <18 years old.
5. All laboratory samples should be collected before administration of study drug.
6. WOCBP only, confirm required contraception use and reminder pregnancy reporting
7. For patients who require HoFH genotyping, stabilization of their lipid-apheresis schedule or stabilization of their background medical LMT, i.e., stable lipid-apheresis for at least 8 weeks before screening and stable background medical LMT for at least 4 weeks (6 weeks for fibrates, 8 weeks for PCSK9 inhibitor antibodies)

Schedule of Events – Screening for Patients with No Run-in

Study Procedure	Screening
Visit	1
Day	-14 to -1
Visit Window (Day)	
Week	-2 to -1
Screening/Baseline:	
Informed Consent	X
	X
Inclusion/Exclusion	X
Medical/Surgical History, Alcohol/Smoking Habits	X
Medication History	X
Demographics	X
Treatment:	
Concomitant Medications (including LMT and apheresis)	X
Query LMT Compliance	X
Efficacy:	
Lipid Panel ^{1,2}	X
Safety:	
Adverse Events	X
Physical Examination	X
Measured Height	X
Body Weight	X
Vital Signs (pulse rate, BP)	X
Electrocardiogram ³	X
Tanner stage ⁴	X
Laboratory Testing⁵:	
Hematology	X
Blood Chemistry	X
Creatine Phosphokinase	X
Hepatitis B Surface Antigen	X
Hepatitis C Antibody	X
Serum Pregnancy Test ⁶	X
Urine Pregnancy Test ⁶	
Sex Hormones ⁴	X
FSH	X
Urinalysis	X
TSH	X
DNA sample for HoFH genotyping	X
Other:	
Review of diet	X

Footnotes for Schedule of Events – Screening for Patients with No Run-in

1. Study assessments will be performed and blood samples will be collected before the dose of study drug in all patients. For patients undergoing apheresis: Study assessments will be performed and blood samples will be collected immediately before the lipid-apheresis procedure; study drug will be administered after the apheresis procedure.
2. Fasting sample will be collected for the lipid panel: total-C, calculated LDL-C, HDL-C, TG, non-HDL-C

3. ECG should be performed before blood samples are collected at visits requiring blood draws.
4. Assessment of Tanner Stage and sex hormones (includes luteinizing hormone, follicle stimulating hormone, estradiol, total testosterone) only applicable to patients <18 years old.
5. All laboratory samples should be collected before administration of study drug.
6. WOCBP only, confirm required contraception use and reminder pregnancy reporting

Schedule of Events – Baseline, Double-Blind Treatment Period, and Open-Label Treatment Period

Study Procedure	Double-Blind Treatment Period								Open-Label Treatment Period					
	2	3	4	5	6	7	8	9 End DBTP ¹⁴	10	11	12	13	14	15 End of OLTP
Day	1	15	29	57	85	113	141	169	197	225	253	281	309	337
Visit Window (Day)	±1	±3	±3	±3	±3	±5	±5	±1	±5	±5	±5	±5	±5	±5
Week	0	2	4	8	12	16	20	24	28	32	36	40	44	48
Baseline:														
Informed Consent	X ¹													
	X ¹													
Treatment:														
Randomization	X ¹													
Administer IV Double-Blind Study Drug	X ¹		X	X	X	X	X							
Administer IV Open-Label Study Drug								X ¹⁰	X	X	X	X	X	
Concomitant Medications (including LMT and apheresis)	X	X	X	X	X	X	X	X	X	X	X	X	X	X
Query LMT Compliance	X ¹	X	X	X	X	X	X	X	X	X	X	X	X	X
Efficacy:														
Lipid Panel ^{2,3}	X	X	X	X	X	X	X	X	X	X	X	X	X	X
Specialty Lipid Panel ^{2,4}	X		X	X	X	X		X		X		X		X
Safety:														
Adverse Events	X	X	X	X	X	X	X	X	X	X	X	X	X	X
Physical Examination								X				X		X
Measured Height														X
Body Weight	X		X	X	X	X	X	X	X	X	X	X	X	X
Vital Signs (pulse rate, BP) ⁵	X	X	X	X	X	X	X	X	X	X	X	X	X	X
Electrocardiogram ⁶								X						X
Tanner stage ⁷								X						X
Confirm contraception use and reminder of pregnancy reporting	X ¹		X	X	X	X	X	X	X	X	X	X	X	X

Study Procedure	Double-Blind Treatment Period								Open-Label Treatment Period					
	2	3	4	5	6	7	8	9 End DBTP ¹⁴	10	11	12	13	14	15 End of OLTP
Day	1	15	29	57	85	113	141	169	197	225	253	281	309	337
Visit Window (Day)	±1	±3	±3	±3	±3	±5	±5	±1	±5	±5	±5	±5	±5	±5
Week	0	2	4	8	12	16	20	24	28	32	36	40	44	48
Laboratory Testing⁸:														
Hematology	X		X	X	X	X		X		X		X		X
Blood Chemistry	X		X	X	X	X		X		X		X		X
Creatine Phosphokinase	X		X	X	X	X		X		X		X		X
Serum Pregnancy Test ⁹														X
Urine Pregnancy Test ⁹	X		X	X	X	X	X	X	X	X	X	X	X	
Sex Hormones ⁷								X						X
Urinalysis	X		X	X	X	X		X		X		X		X
hs-CRP	X							X						X
HbA1C	X ¹				X			X			X			X
LDLR function	X ¹													
Research Samples	X ¹		X	X		X		X	X					
PK and PD Samples														
ADA Sample ¹⁰	X ¹		X		X			X						X
PK (evinacumab, alirocumab), ANGPTL3, PCSK9 Samples ^{11,12}	X ¹	X	X	X	X	X	X	X			X			X
PK of statin ¹¹	X ¹					X								
DNA sample for HoFH genotyping	X ¹													
XXXXXXXXXX	X ¹													
Other:														
EQ-5D	X							X						
HADS	X ¹							X				X ¹⁵		X ¹⁵
Review of diet	X ¹	X	X	X	X	X	X	X	X	X	X	X	X	X

Footnotes for Schedule of Events – Baseline, Double-Blind Treatment Period, and Open-Label Treatment Period

1. For those patients enrolling directly from the R727-CL-1628 study and do not complete the R1500-CL-1629 run-in or screening period, the informed consent forms should be signed at the baseline visit. Overlapping assessments completed at the R727-CL-1628 open-label EOT visit do not need to be duplicated during the R1500-CL-1629 baseline visit; only assessments footnoted will need to be performed.
2. Study assessments will be performed and blood samples will be collected before the dose of study drug in all patients. For patients undergoing apheresis: Study assessments will be performed and blood samples will be collected immediately before the lipid-apheresis procedure; study drug will be administered after the apheresis procedure. The timing between the baseline sample collection relative to the most recently completed LDL apheresis procedure, administration of a PCSK9 inhibitor or mipomersen should match the timing of the week 24 sample collection relative to the most recently completed LDL apheresis procedure, administration of a PCSK9 inhibitor or mipomersen. Depending on the duration between the LDL apheresis procedure and sample collection, the visit window may not apply.
3. Fasting sample will be collected for the lipid panel: total-C, calculated LDL-C, HDL-C, TG, non-HDL-C
4. Fasting sample will be collected for specialty lipid panel: Apo B, Apo A-1, and Lp(a)
5. On dosing days, vital signs should be recorded prior to IV infusion, and 30 minutes and 60 minutes post-IV infusion
6. ECG should be performed before blood samples are collected at visits requiring blood draws.
7. Assessment of Tanner Stage and sex hormones (includes luteinizing hormone, follicle stimulating hormone, estradiol, total testosterone) only applicable to patients <18 years old.
8. All laboratory samples should be collected before administration of study drug.
9. WOCBP only, confirm required contraception use and reminder pregnancy reporting
10. The ADA sample should be drawn before study drug administration
11. For patients who are not undergoing apheresis, the PK sample should be drawn before the dose of study drug and at the end of the infusion. For patients undergoing apheresis, a PK sample should be collected immediately before the apheresis procedure and a PK sample should be collected immediately after the apheresis procedure, prior to administration of study drug, and, again at the end of the infusion of study drug.
12. Including assay of total ANGPTL3.
13. Should be collected at the baseline visit, or at any study visit
14. All end of treatment (EOT) assessments will be performed and blood samples will be collected before the dose of open-label study drug in all patients. For patients undergoing

apheresis: Study assessments will be performed and blood samples will be collected immediately before the lipid-apheresis procedure; open-label study drug will be administered after the apheresis procedure.

15. In the OLTP, the HADS should be administered after the patients have been informed of their lipid results.

Schedule of Events – Follow-up Period

Study Procedure	Follow-up Period ⁵				
	16 ⁵	PV17 ^{5,6}	18 ⁵	PV19 ^{5,6}	EOS 20
Visit					
Day	365	393	421	449	477
Visit Window (Day)	±5	±5	±5	±5	±5
Week	52	56	60	64	68
Treatment:					
Concomitant Medications (including LMT and apheresis)	X	X	X	X	X
Query LMT Compliance	X	X	X	X	X
Safety:					
Adverse Events	X	X	X	X	X
Physical Examination					X
Measured Height					
Body Weight					X
Vital Signs (pulse rate, BP)					X
Electrocardiogram ¹					X
Tanner stage ²					X
Confirm contraception use and reminder of pregnancy reporting	X	X	X	X	X
Laboratory Testing:					
Lipid Panel	X		X		X
Specialty Lipid Panel	X		X		X
Hematology	X		X		X
Blood Chemistry	X		X		X
Creatine Phosphokinase	X		X		X
Serum Pregnancy Test ³					X
Urine Pregnancy Test ³	X	X	X	X	
Sex Hormones ²					X
Urinalysis					X
hs-CRP					X
HbA1C			X		X
PK and PD Samples					
ADA Sample					X
PK (evinacumab, alirocumab), ANGPTL3 Samples ⁴					X
Other:					
Review of diet					X

Footnotes for Schedule of Events –Follow-up Period

1. ECG should be performed before blood samples are collected at visits requiring blood draws.
2. Assessment of Tanner Stage and sex hormones (includes luteinizing hormone, follicle stimulating hormone, estradiol, total testosterone) only applicable to patients <18 years old.
3. WOCBP only, confirm required contraception use and reminder pregnancy reporting.
4. Including assay of total ANGPTL3.
5. For patients who discontinue prematurely or who opt out of the OL study.
6. Phone visits (PV) at weeks 56 and 64 to confirm required contraception use and obtain results of the home urine pregnancy test. Adverse events and concomitant medications will be collected.

Signature Page for VV-RIM-00083002 v1.0

ESig Approval	 15-Jul-2019 19:05:13 GMT+0000
ESig Approval	 15-Jul-2019 19:10:18 GMT+0000
ESig Approval	 15-Jul-2019 20:13:15 GMT+0000
ESig Approval	 16-Jul-2019 14:30:20 GMT+0000
ESig Approval	 16-Jul-2019 17:03:13 GMT+0000

Signature Page for VV-RIM-00083002 v1.0 Approved
